7.2. Procedures for Recording and Reporting Adverse Events

Fatal or life-threatening events thought to be caused by Study Drug will be reported to the Chair

of the DSMB and the MUSC IRB. There are no events that are expected to occur as a result of AAT or placebo infusion.

Serious AEs require expedited reporting to the DSMB Chair or designee, regardless of the relationship of the event to the study treatment regimen. Refer to the previous section for the definition of a serious adverse event.

Investigators will report all SAEs to the DSMB Chair or designee within the timelines of NIDDK policy after observation or learning of the event. For initial SAE reports, the Investigator should record all case details that can be garnered on the SAE form and the AE CRF page. Relevant follow-up information is to be submitted to the Sponsor or its designee as soon as it becomes available.

Adverse Events will be reported to the IRB and the NIDDK program officer. The DSMB will review all safety data and all adverse events that occur (see section 7.3). The MUSC Internal Review Board will also monitor this study.

7.2.2. Special Reporting Situations

- **Death:** Death is an outcome of an event. The event that resulted in death should be recorded and reported on the SAE form and the AE CRF page.
- **Hospitalization for Surgical or Diagnostic Procedures:** The illness leading to the surgical or diagnostic procedure is to be recorded as the SAE, not the procedure itself. The procedure is to be captured in the case narrative as part of the action taken in response to the illness.

7.3. Data Safety Monitoring Board (DSMB):

DSMC recommended by the NIDDK will meet to approve the protocol and the statistical plan before patient recruitment. The DSMC meeting frequency will be determined by the NIDDK. We suggest that the committee meet after the 5th patient has been treated, so that safety issues can be discussed. We will send quarterly SAE/AE reports to the committee according to the safety procedures described above. Safety procedures have been in place for our current islet autotransplantation procedure at MUSC. Any Suspected Unexpected Serious Adverse Reaction will lead to interruption of study recruitment until the DSMC has reviewed and approved recommencing. An update of the progress of the study including an efficacy and safety report be submitted to the DSMB every 6 months during the conduction of the study and a report at the end of it.

8. STATISTICAL ANALYSIS:

8.1. STATISTICAL ANALYSIS PLAN AND STATISTICAL REPORTS

The following section provides the details of statistical analyses planned, including safety and primary and secondary efficacy endpoints. In addition, it discusses the statistical issues relevant to these analyses (e.g., sample data to be used, missing data).

The Statistical and Data Management Center (SDMC) generates a closed statistical report to be distributed only to the DSMB. The timing of the report is determined in consultation with the DSMB. Reports will be sent from the SDMC to the NIDDK two weeks in advance of the scheduled meeting.

Each report provides cumulative summary statistics on enrollment; subject status in the study; baseline characteristics; protocol violations; safety data, including AEs and SAEs, severity, expectedness and relatedness to the study treatment; and data management/quality information (e.g., timeliness and completeness of data entry; number of data clarification requests generated and resolved). The statistics are provided for the overall study in the open report. For the closed report only, the statistics are also provided by partially blinded treatment groups (A vs B). Due to the unequal allocation used in this study, partially blinded reports will not include the counts.

8.2. ANALYSIS POPULATION:

8.2.1. MODIFIED INTENT-TO-TREAT POPULATION

The modified intent-to-treat (mITT) population includes all randomized subjects who meet study eligibility criteria and have received at least one injection (of AAT or placebo). The primary efficacy measures will be analyzed with the mITT population.

8.2.2. PER-PROTOCOL POPULATION

The per-protocol (PP) population includes all randomized subjects who meet the study eligibility criteria, completed the assigned treatment infusions, and have the primary efficacy endpoint assessed.

8.2.3 SAFETY POPULATION

The safety population (SP) includes all subjects for whom consent is obtained and surgery is performed.

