1.1. PROTOCOL SYNOPOSIS

Study Sponsor	NIH/NIDDK	
Investigational Product	Alpha-1 antitrypsin (AAT)	
Indication	Patients with chronic pancreatitis	
Title of Study	AAT Enhances Islet Autograft Survival	
Protocol Date	12/01/15	

OBJECTIVES

Primary objective: To describe and compare the safety and efficacy of treatment with AAT in chronic pancreatitis patients who undergo total pancreatectomy and islet autotransplantation (TP-IAT).

METHODOLOGY

Study Design	Prospective, controlled, double-blind
Treatments	Recipients will receive AAT before and post islet transplantation
Treatment Duration	Recipients will receive a total of 4 weekly infusions of AAT or placebo.
Study Drug and Formulation	Prolastin-C (Grifols)
Dose and Route of Administration	
 • AAT 60 mg/kg (IV) • Placebo- 0.9 % sodium chloride (IV). 
The first dose will be given on the day of islet transplantation before total pancreatectomy (D0), and then on days 7, 14, and 21 days of islet transplantation.

Number Planned	48
Major Inclusion Criteria	
 • Patients scheduled for total pancreatectomy and islet autotransplantation • Age > 18 years • Diabetes free before surgery

Exclusion Criteria	
 • Patients who are under immunosuppression • Patients who have had puestow or frey pancreatic surgery • Patients who have Immunoglobulin A (IgA) deficiency, known antibodies against IgA, or individuals with a history of severe immediate hypersensitivity reactions, including anaphylaxis to Alpha₁-proteinase inhibitor products (allergic to AAT)
Safety	
 • Physical examination, hematology, serum chemistry, urinalysis, vital signs, adverse event (AE) monitoring, and concomitant medications.
Efficacy	Efficacy of AAT therapy during peri-transplant period in chronic pancreatitis patients who undergo TP-IAT as assessed through islet function, onset of diabetes, glycemic control, pain relief and quality of life measurements.
ENDPOINTS	
Primary Endpoint	Area under the curve for the serum C-peptide level during the first 4 hours of an mixed meal tolerance test (MMTT), normalized by the number of islet equivalents (IEQ)/kg at day 365±14 after the transplant.

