2.3.4. Other study related procedures

All other procedures including islet transplantation, c-peptide, and glucose testing are part of standard patient care and would be performed regardless of study participation.

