6.1. HOSPITAL STAY

6.1.1. Patient recruitment, blinding and randomization

Subjects will be recruited from the clinical offices of Drs. [name] and [name] during their routine preoperative evaluation for pancreas resection and islet transplantation. During their preoperative evaluation, the purpose of the study and the associated consent form will be explained in detail and the participant will be given time to ask questions. If the subject wishes to participate, the proper consent and HIPAA forms will be signed and dated. The consent form may be signed in person in a clinic or via telehealth using an eConsent/doxy.me. On the doxy.me platform the study participant has the ability to download a copy of the signed consent for their record. They will be informed of this and encouraged to download their copy by the study team member who is obtaining consent. The virtual visit video chat feature of this platform allows for questions from the patient to be answered in real time by the study team. The study team member obtaining consent will also have the ability to review the HIPAA authorization form with the patient and obtain a signature through the doxy.me platform. A copy of the signed consent form will accompany the patient to the operating room for documentation of participation in the study.

Consented patients will be screened based on inclusion and exclusion criteria. If patient meets the criteria, they will be randomized to either AAT or control group by block randomization. The PI ([name]) and the clinical PIs ([name], [name], [name], [name]) of this study will be blinded for the assignment of the study treatment. The Investigational Pharmacy at MUSC will prepare drug infusions using aseptic technique under a sterile hood. In the clinic, a trained RN will infuse the drug and monitor for side effects of AAT. These individuals will not be blinded.

Diabetes care will be managed by the Endocrinology team at MUSC led by [name], co-investigator of our trial. The diabetes care is standardized while in the hospital with insulin drip for all patients post-operatively. The drip is then weaned over the first few days with care individualized by the hospital diabetes management team. The discharge plan is then individualized in accordance with ADA standards.

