6.1.2 Infusion of the Investigational Product

Infusion of AAT will start on the day of islet transplantation before anesthesia and pancreatectomy, which is approximately 6-8 hours before islet infusion. The clinical PIs, Drs. [name] and [name], will identify the time to start the study drug infusion. Starting and ending time of drug administration, amount of drug infused, and infusion rate will be recorded for each subject. On Average, TP-IAT patients stay in the hospital for 7-28 days after islet transplantation. If they stay till 21 days post transplantation, they can have all four AAT injections in the hospital. If they are discharged earlier, patients will be requested to return to MUSC for additional drug infusion(s). A nurse will administer the AAT or placebo infusion to the patient while in the hospital. A nurse in the GI surgery clinic or SCTR outpatient clinic will administer AAT or placebo to patients discharged but returning for one of the weekly visits. The nurses infusing these drugs will be trained on the day of administration concerning the few known side effects of AAT and rate of infusion.

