8.10. SAFETY ANALYSES

Study subjects will be asked to report any and all AEs/new symptoms at any time from study enrollment until 52 weeks after study treatment, whether or not they attribute them to the study intervention or procedures. Subjects, who discontinue the study treatment regimen for any reason, including subjects who are treatment failures due to unable to return for some of the treatment injection(s) will be encouraged to attend the remaining visits for assessment of safety, secondary and pharmacokinetic endpoints.

To assess safety in this population, vital signs will be performed at each of the study visits. Additionally, medical history will be collected at screening and baseline and adverse events occurring after start of study therapy will be recorded.

Since the safety endpoints are primarily binary indicators for each subject (e.g. experiencing a particular AE during the 24-weeks post-treatment), their analyses will involve logistic regression models. For certain safety endpoints, it may be more appropriate for them to be analyzed using survival techniques, which are more suitable for time-to-event data than logistic regression. In such circumstances, Cox proportional hazards models will be used to compare treatment arms; however, should the proportionality assumptions not hold, alternative strategies (e.g. stratified analyses) will be used. The safety analyses will be conducted in the Safety Population.

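### The safety population is defined by consent and surgery, not by receipt of study drug, so the final adverse-event analysis can omit a dosed patient and count an undosed one

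*Combined protocol and SAP*

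**What the plan says.** Section 8.2.3 sets two conditions for the safety population: "The safety population (SP) includes all subjects for whom consent is obtained and surgery is performed". It mentions neither randomization nor study drug. Section 8.10 then says: "The safety analyses will be conducted in the Safety Population".

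On timing, section 6.1.2 states: "Infusion of AAT will start on the day of islet transplantation before anesthesia and pancreatectomy". The synopsis, section 3.1 and the schedule in Appendix 1 also place the first infusion before surgery.

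The modified intent-to-treat set in section 8.2.1 does require at least one infusion of either product, but it serves another purpose: "The primary efficacy measures will be analyzed with the mITT population".

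Two further statements bear on who can enter the safety set. Section 6.1.1 puts consent ahead of eligibility checks: "Consented patients will be screened based on inclusion and exclusion criteria". Section 2.3.4 says that islet transplantation and the other procedures it lists "are part of standard patient care and would be performed regardless of study participation".

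**The concern.** A safety set for adverse events should contain the people who were exposed. Here, surgery comes after the first dose and decides who is in. If the operation is called off because of a reaction to that first infusion, the set loses the event most plausibly related to the drug. The exclusion is informative only in that situation; a cancellation for an unrelated reason costs a patient but need not bias the rate.

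In the other direction, the wording admits people who never received AAT or placebo, including some who were never assigned to an arm.

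Describing and comparing the safety of AAT is part of the study objective in section 3.4, and section 8.3 says the estimates will be used to design a larger trial. What is at stake is therefore the reported adverse-event rate in the AAT arm and its upper confidence limit.

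**Working it through.** The plan gives no figure to reproduce here. The check sets the definitions against the order of events, then illustrates the size.

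**Order of events.** Consent, screening and randomization (6.1.1); first infusion, then anesthesia and pancreatectomy (6.1.2); islet infusion about 6-8 hours after the first dose (6.1.2).

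**Who falls where.**

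| Patient path | mITT set (8.2.1) | Safety set (8.2.3) |
|---|---|---|
| Eligible, dosed, operated on | in | in |
| Eligible, dosed, not operated on | in | **out** |
| Randomized, not dosed, operated on | out | **in** |
| Consented, fails screening, operated on as standard care | out | **in**, with no arm |

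The second row is the omission. The mITT set holds that patient but is assigned to efficacy, and no other section returns the patient to the section 8.10 analysis. The last two rows are the unwanted inclusions. Sections 8.2.1 and 8.2.2 restrict their sets to randomized subjects; section 8.2.3 does not.

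**Size of the omission (illustration; the documents give no rate).** Inputs: 32 AAT and 16 placebo patients (section 3.1). Assume that one AAT patient has a serious reaction to the first dose, is not operated on, and is the only patient in the arm with such an event.

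- All dosed patients: 1/32 = 3.1%. The exact (Clopper-Pearson) 95% upper limit solves (1 − p)^32 + 32p(1 − p)^31 = 0.025, giving p = 16.2%.
- Safety set as written: 0/31 = 0%. The upper limit is 1 − 0.025^(1/31) = 11.2%.
- Test against 0/16 placebo: with one event among 48 patients, the two possible tables have probabilities 32/48 and 16/48. The observed table is the likelier one, so Fisher's two-sided p = 1.0. With no events in 31 and 16, p = 1.0 again.

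**Chance that any patient is dosed but not operated on.** With an assumed per-patient probability d, the chance of at least one among 48 is 1 − (1 − d)^48.

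| Assumed d | Chance of at least one |
|---|---|
| 1% | 38% |
| 2% | 62% |
| 5% | 91% |

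These values of d have no basis in the documents. They cover non-surgery for any reason, with or without an adverse event, so they do not measure bias.

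**Size of the inclusion.** If one of 32 AAT-assigned patients is operated on but never dosed, one event among the 31 dosed patients is reported as 1/32 = 3.1% instead of 1/31 = 3.2%.

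**The case against.** The strongest reply is that the gap is narrow and that no event goes unseen. The infusion takes 15-30 minutes and surgery is planned for the same day, so few patients should be dosed and then not operated on. Section 4.2 excludes IgA deficiency and previous severe hypersensitivity to the product class, and IgA is measured at screening. Section 2.3.2 reports a rash as the most serious reaction in Prolastin-C studies, although in a different population. Serious events go to the DSMB whatever their cause (7.2), a suspected unexpected serious reaction interrupts recruitment (7.3), and the DSMB also receives a report at the end of the study. Most other safety endpoints are timed to discharge or to days 75-365 after transplant, so for an unoperated patient essentially only adverse events are affected. All of this stands and limits the severity. None of it puts the omitted patient into the final section 8.10 analysis.

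The inclusion side can be attacked separately. Section 7.1.1 defines an adverse event in terms of someone given an investigational drug, so an undosed patient arguably contributes no event, and a screen failure has no arm to be compared in. But section 8.10 also asks for events from enrollment onward. Even on the strict definition, an undosed patient who was randomized would still sit in the denominator. The wording remains wrong, with negligible numerical effect.

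Finally, no misallocation of treatment has been shown, so analysis by treatment received may look like an extra. It belongs in the definition because an exposure-based set needs a rule for assigning patients to arms, and the plan states none for safety.

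**Conclusion.** The concern holds and is minor. As written, the population for the final adverse-event analysis is selected on an event after the first dose and does not require exposure. The omission of a dosed, unoperated patient is the part that matters: under the illustrative assumption of one such patient with a serious reaction, the AAT rate moves from 3.1% to 0% and its upper limit from 16.2% to 11.2%. A between-arm test does not change, and section 8.3 treats all hypothesis testing as exploratory. The counting of undosed patients is an error of definition with almost no effect on the rates. The conclusion about the wording rests only on the text; the sizes rest on assumed counts. Monitoring of patients during the trial is unaffected.

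**What to change.** In section 8.2.3, define the safety population for adverse and serious adverse events as all subjects who received any amount of AAT or placebo, analysed by treatment received, whether or not surgery followed. Add a sentence saying that endpoints with meaning only after pancreatectomy, such as steatorrhea and the laboratory values at post-transplant discharge, are summarised in the operated subset of that population. Events in consented but undosed subjects can be listed separately.

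The cost is two sentences in section 8.2.3, plus a listing if wanted. No new data are needed: section 8.10 already calls for recording events once study therapy has begun, and Appendix 1 includes adverse-event recording at the baseline visit before surgery.

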8.3. SAMPLE SIZE JUSTIFICATION

We recognize that the number of participants is small given the heterogeneity of chronic pancreatitis but believe the numbers are appropriate for a proof-of-concept translational study. The goal of this aim would be to test whether IAT + AAT is feasible in this patient population and to obtain preliminary assessments of its success. Having n=32 subjects treated with AAT

(and n=16 placebo controls) would allow us to make relatively precise estimates of feasibility measures and means of the study outcomes, with 95% confidence intervals that would extend approximately 0.3 standard deviation units in either direction. While recognizing that the standard deviation will be slightly higher in the control population, we recognize that all hypothesis testing will be considered exploratory, enabling 80% power to detect moderately large differences (effect sizes of 0.9 standard deviation units) between the AAT and treated control groups with respect to the study outcomes, including the 4 hour C-peptide level AUC obtained at 12 months, assuming up to a 10% loss to follow-up over the 12 months. Having these numbers of subjects would also allow us to make preliminary comparisons between outcomes in the IAT + AAT group and outcomes observed in a group of 150 historical controls, each of whom received a total pancreatectomy with IAT at MUSC from 2009-2015. Most importantly, the data (e.g. means, standard deviations, and effect size estimates) from 32 subjects receiving AAT treatment, 16 control subjects receiving islets alone, and 150 historical controls will be vital for use in designing a larger more definitive randomized controlled trial in the future. Using 2:1 randomization will help provide more precise estimates of outcomes in the IAT + ATT group and may also help with study recruitment, as subjects may tend to be more willing to consent if they have a stronger probability of receiving the active experimental treatment.

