3.2. STUDY TIME TABLE

Planned patients are expected to be recruited in a 36-month period. A follow-up of 12 months is planned for each patient. The overall timelines are as below:

- Projected starting date (first-patient-in): June 1, 2016
- Projected completion of patient accrual (last-patient-in): May 31, 2019
- Projected study end date: May 31, 2020

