The required lab tests for the study include an IgA level and the MMTT at time 75 and 365 days. There are no imaging screening tests required for this study. It is noted that many of the safety laboratories will be the same laboratory assessments as are used for the usual surgical care.

One basal serum sample will be collected prior the first infusion of study drug (AAT or normal saline) and be stored for pre-transplant chemokines/cytokines. The basal sample will be obtained before surgery.

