8.9. EFFICACY ANALYSES

The primary efficacy analyses will involve the use a general linear mixed model (GLMM) to test whether the primary endpoints differ over time between subjects assigned to the AAT arm when compared to subjects assigned to placebo. The analysis will be performed on the mITT and PP populations, although the analyses within the mITT population will be considered primary.

Contrasts will be constructed to estimate the AAT treatment effect on outcomes at day 75 and at day 365. To account for the fact that observations within the same subjects will be correlated, various error covariance structures will be considered, including unstructured, autoregressive, and compound symmetry. If model assumptions are not met (e.g. normality) alternative strategies will be utilized, including transformations of dependent variables and non-parametric alternatives. Any pre-transplantation subject characteristics be found to be significantly different between the study subjects and historical controls will be included as covariates for all between-group comparisons. Model fit will be assessed using criteria such as Akaike Information Criterion. All primary and secondary outcomes will be reported in study communications.

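### In the AAT-versus-historical comparison, calendar period is fully confounded with AAT and the planned covariates cannot remove it; report placebo minus historical beside it and take the future effect size from the randomised contrast.

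*Combined protocol and SAP*

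**What the plan says.** Section 8.3 (Sample size justification) introduces a second comparison beside the randomised one: "preliminary comparisons between outcomes in the IAT + AAT group and outcomes observed in a group of 150 historical controls". These are earlier patients of the same centre, transplanted in 2009-2015. The section then names the data that will feed the design of a larger trial, including means, standard deviations and effect-size estimates, and lists their sources as "32 subjects receiving AAT treatment, 16 control subjects receiving islets alone, and 150 historical controls". It does not say which contrast will supply the effect size.

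Section 3.2 (Study time table) gives the trial's period: "Projected starting date (first-patient-in): June 1, 2016".

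Section 8.9 (Efficacy analyses) makes the primary efficacy analysis a comparison of "subjects assigned to the AAT arm when compared to subjects assigned to placebo". It also holds the only rule for handling differences from the historical group: "Any pre-transplantation subject characteristics be found to be significantly different between the study subjects and historical controls will be included as covariates".

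On measurement, section 6.1.1 states: "The required lab tests for the study include an IgA level and the MMTT at time 75 and 365 days". Section 6.3.6 specifies eight samples over 240 minutes, with ±14-day windows. Section 2.3.4 says that "c-peptide, and glucose testing are part of standard patient care and would be performed regardless of study participation". No section describes how outcomes of the 150 historical patients were obtained: source, test, assay and timing are all unstated.

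**The concern.** Every historical patient precedes every trial patient. In AAT minus historical, treatment and calendar period are therefore the same variable, and the contrast estimates the AAT effect plus whatever else changed at the centre. A change in islet isolation or counting, diabetes management, C-peptide assay or follow-up practice is not a pre-transplantation patient characteristic, so the rule in 8.9 does not reach it. The bias equals the full drift, and more historical patients do not shrink it.

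The placebo arm shares the AAT arm's period, visits and tests, so it is the one group that can separate drift from drug. No placebo-versus-historical contrast is named.

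At stake is the planning of the next trial. A biased estimate could enter its design as an AAT effect, or drift in the other direction could make a useful treatment look inactive.

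**Working it through.** **Inputs.** Group sizes of 32, 16 and 150, and 10% loss over 12 months (8.3). After loss: 32 × 0.9 = 28.8 and 16 × 0.9 = 14.4. The 150 are kept whole. Assumptions: two-sided 5% level (8.3 states none for its power figure; the plan uses 95% intervals), normal approximation, and a common SD. Section 8.3 expects a slightly larger SD in controls, which is ignored here. Drift is written δ, in SD units. The documents give no value for it, so a range is shown.

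**Step 1: the plan's own figure.** SE(AAT − placebo) = √(1/28.8 + 1/14.4) = 0.323. Power at 0.9 SD = Φ(0.9/0.3227 − 1.96) = Φ(0.829) = 79.6%, which reproduces the stated 80%. The plan gives no power or precision for the historical comparison.

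**Step 2: what each contrast estimates.** With a true AAT effect τ:
- AAT − placebo estimates τ
- AAT − historical estimates τ + δ
- placebo − historical estimates δ

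A drift common to both trial arms cancels in the first contrast and stays whole in the second.

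**Step 3: standard errors.**
- AAT − historical: √(1/32 + 1/150) = 0.195; after loss √(1/28.8 + 1/150) = 0.203
- Placebo − historical: √(1/16 + 1/150) = 0.263; after loss √(1/14.4 + 1/150) = 0.276
- AAT − placebo: √(1/32 + 1/16) = 0.306; after loss 0.323

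**Step 4: chance of nominal significance when τ = 0.** P = Φ(δ/SE − 1.96) + Φ(−δ/SE − 1.96). For example, δ = 0.3 after loss gives Φ(0.3/0.2034 − 1.96) = Φ(−0.485) = 31%; the other tail is negligible.

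| Assumed δ (SD) | AAT − historical, no loss | AAT − historical, 10% loss | Placebo − historical, no loss | Placebo − historical, 10% loss |
|---|---|---|---|---|
| 0 | 5% | 5% | 5% | 5% |
| 0.2 | 18% | 17% | 12% | 11% |
| 0.3 | 34% | 31% | 21% | 19% |
| 0.5 | 73% | 69% | 48% | 44% |

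The last two columns are the power of the placebo arm to detect the same drift.

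**Step 5: precision of the drift estimate.** The 95% half-width is 1.96 × 0.263 = 0.52 SD, or 1.96 × 0.276 = 0.54 SD after loss. For 80% power the drift must be about 2.80 × 0.263 = 0.74 SD, or 2.80 × 0.276 = 0.77 SD after loss.

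**Step 6: fewer usable historical patients.** If only 50 had a matching measurement (an assumption), SE = √(1/28.8 + 1/50) = 0.234, and the 31% at δ = 0.3 becomes about 25%. The bias is still δ.

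**The case against.** The strongest reply is that this is a side comparison. Section 8.3 calls it preliminary and treats all hypothesis testing as exploratory, the primary analysis is randomised, and no success rule rests on the historical group. That stands, and it limits the importance of the point. It does not answer the planning use, because 8.3 puts the historical data among those it most wants for the next design.

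Four stronger readings are tempting, and the documents do not support them:
- A reader might infer that protocol MMTTs are being set against routine-care records. The historical test and source are undescribed, so a measurement difference is possible but not shown. For SF-12 and narcotic dose, even the trial data come from an existing outcomes database (6.3).
- A reader might infer that the next trial's effect size will be AAT minus historical. Section 8.3 names all three groups and does not choose.
- A reader might infer that the plan excludes a placebo-historical comparison. It is unnamed, not excluded; the covariate rule in 8.9 speaks of study subjects in general.
- A reader might infer that the tighter standard error alone makes false positives more likely. Without drift the rate stays at 5%.

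Continuity is also argued: same centre, transplant procedures kept at the centre's routine (3.1), and an endpoint normalised by IEQ/kg (3.5.1). These help in part. Section 3.1 does not say that the routine was constant from 2009, and a change in islet counting would enter through the denominator.

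Finally, the placebo check is weak. That is correct, and it governs how the check should be reported.

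**Conclusion.** The point holds for the AAT-versus-historical contrast only. Period and AAT are completely confounded there, the planned covariates cannot separate them, and no contrast is named that would estimate the drift. That much follows from the dates and the text of 8.3 and 8.9. How often it would mislead depends on an assumed drift: over 0.2 to 0.5 SD, a null treatment would look nominally significant in roughly one trial in six to two in three, with all 150 historical patients usable. The direction of any drift is unknown. The randomised result is not in question. This is a worthwhile, low-cost correction to a preliminary analysis, not a flaw in the primary one.

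**What to change.** In 8.3 and 8.9:

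1. Fit the AAT, placebo and historical groups in one model with the same covariates. Report placebo minus historical with its 95% CI beside AAT minus historical, as an estimate of drift and not as a pass/fail test.
2. Describe the historical outcome source, test, assay and timing. Limit each historical comparison to outcomes obtained by the same test within the day-75 or day-365 window, and report how many of the 150 qualify for each outcome.
3. State that the effect size for the future trial comes from the randomised AAT-minus-placebo contrast, and that no efficacy statement will rest on AAT minus historical alone.

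The cost is SAP wording, one extra contrast and a check of the historical records; no new patients or visits are needed. There are two downsides. The drift interval will be wide, so one that includes zero must not be read as showing that the historical comparison is sound. And the usable historical group may be smaller than 150, particularly for the MMTT endpoint.
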